6.2 Exclusion criteria

1. Liver disease other than CHB (a diagnosis of steatosis is permitted providing inclusion criterion 6 is met).
2. Evidence of Liver cirrhosis on Fibroscan at screening (Liver cirrhosis is defined as a Fibroscan measurement of >11.5 KPa), or previous history or evidence of cirrhosis on radiological imaging, Fibroscan or liver biopsy.
3. Positive serology for HIV-1 or HIV-2 or HCV or HDV antibodies.
4. Immunodeficient or autoimmune conditions due to disease or medication e.g. systemic steroids within previous 12 weeks. (Topical or inhaled steroids are permissible).
5. Clinically relevant co-morbidity, e.g. autoimmune disease.
6. Clinically relevant anaemia or leukopenia in the opinion of the investigator.
7. Cancer or treatment for cancer within 3 years prior to screening excluding basal cell carcinoma of the skin, which is allowed.
8. Known or suspected intolerance or hypersensitivity to the IMP or closely related compounds or any of the stated ingredients.
9. Receipt of any IMP within 90 days prior to screening or currently receiving IMP or intent to receive IMP.
10. Current substance or alcohol abuse that in the opinion of the Investigator would interfere with compliance or with interpretation of study results.
11. Any condition that in the opinion of the Investigator might interfere with study objectives.
12. Pregnant or breastfeeding.
13. Subjects should not have received, during the 6 month period prior to screening, any medications or other treatments that may adversely affect the immune system such as allergy injections, immunoglobulins, interferons, cytotoxic drugs or other drugs known to be frequently associated with significant major organ toxicity, or systemic corticosteroids (oral or injectable).
Immunosuppressive treatment such as azathioprine or mercaptopurine is not permitted in the 6 months prior to screening.
14. Administration of live vaccines (such as live influenza vaccinations or live travel vaccinations) from 10 days prior to the screening visit until Day 85.

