10.3 Statistical analysis plan

The proposed statistical analyses for this study will be detailed in a separate statistical analysis plan (SAP), which will be finalised prior to database lock. Any changes to the statistical analysis described in this protocol do not require a protocol amendment but must be described as a 'change to the protocol planned statistical analysis' in the SAP and the clinical study report.

The statistical analysis and report will conform to the relevant ICH requirements.

Data listings and summary tables will be generated using the software SAS® Version 9.3 or later. All data recorded in the eCRFs will be included in data listings. The SAS datasets and programs will be made available to the Sponsor at study closure.

Summary tables and data listings will be presented by treatment arm and time point.

The standard summary statistics for continuous variables will comprise number of valid observations, arithmetic mean, standard deviation, median, quartiles, minimum, and maximum. The geometric mean and coefficient of variation will also be presented for continuous variables which are positive and substantively positively skewed (such as liver enzyme levels, ELISpot counts and measures of viral load). The standard summary statistics for categorical data will comprise absolute and relative frequencies (proportions).

If continuous variables are assessed both at and after baseline, change from baseline will be calculated and summarised. If categorical variables are assessed both at and after baseline, then cross-tabulations will be presented by category at baseline.

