### 12.6.3 Laboratory Data

Descriptive statistics for clinical laboratory values (in SI units) and changes from baseline at each assessment time point will be presented by treatment group for the following clinical laboratory variables in [Table 6](#).

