**Table 6: Clinical laboratory safety test analytes to be presented in summary tables**

Panel	Parameters	
Haematology	White blood cells (leukocytes)	Neutrophils [a]
	Red blood cells (erythrocytes)	Lymphocytes [a]
	Haemoglobin	Monocytes [a]
	Haematocrit	Eosinophils [a]
	Mean corpuscular volume	Basophils [a]
	Mean corpuscular haemoglobin	Platelets
	Mean corpuscular haemoglobin concentration	
Serum biochemistry	Sodium	Aspartate transaminase (AST)
	Potassium	Alkaline phosphatase (ALP)[b]
	Urea	Alanine aminotransferase (ALT)
	Creatinine	Creatine kinase [c]
	Albumin	Gamma-glutamyl transferase (gamma glutamyl transpeptidase) (GGT)
	Calcium	Lactate dehydrogenase
	Phosphate	Total and direct bilirubin
	Glucose	
	Total protein	
	C-reactive protein	
Coagulation	International normalised ratio of prothrombin time (INR)	
Urinalysis	Protein	Leukocyte esterase
	Bilirubin	Red blood cells
	Urobilinogen	pH
	Ketones	Nitrites
	Glucose	Specific gravity

[a] Given as both absolute count and as a percentage of total leukocyte count. In cases where only absolute counts or percentages of these leukocyte subtypes are recorded, the missing percentage or absolute count will be derived.

[b] Alkaline phosphatase iso-enzymes (liver-specific and bile duct specific) will be measured if original alkaline phosphatase test result is above the upper limit of normal.

[c] Creatine kinase MB or Troponin T will be measured where clinically indicated.

In addition, if protein and/or blood is/are detected during urinalysis then a microscopic examination will be conducted consisting of leukocytes, erythrocytes, casts and bacteria.

Laboratory results will be categorised as low, normal or high in relation to the local laboratory reference range, and shift tables from baseline to each time point will be presented.

Clinical laboratory test values are assessed for clinical significance by the investigator. The number and percentage of subjects with post-baseline clinically significant values will be tabulated by treatment group. The percentages will be calculated relative to the number of subjects with at least 1 post-baseline assessment.

All laboratory results will be listed, including microscopic urinalysis results if collected.

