Table 14.2.2.2	Qualitative Virology Results by Time Point - HBsAb	Immunogenicity Analysis Set	
Table 14.2.2.3	Quantitative Virology Results by Time Point - HBsAg and HBV DNA	Full Analysis Set	X
Table 14.2.2.4	Qualitative Virology Results by Time Point - HBsAb	Full Analysis Set	
Figure 14.2.2.5	Line Plot of Change from Baseline in log10 HBsAg at each Timepoint by Treatment Group	Immunogenicity Analysis Set	
Figure 14.2.2.6	Line Plot of Change from Baseline in log10 HBsAg at each Timepoint by Treatment Group	Full Analysis Set	
Table 14.3.1.1	Summary of Investigational Product Exposure	Safety Analysis Set	
Table 14.3.2.1	Overall Summary of Adverse Events	Safety Analysis Set	
Table 14.3.2.2	Treatment-emergent Adverse Events by System Organ Class and Preferred Term	Safety Analysis Set	X
Table 14.3.2.3	Treatment-emergent Adverse Events by System Organ Class and Maximum Severity	Safety Analysis Set	
Table 14.3.2.4	Serious Adverse Events by System Organ Class and Preferred Term	Safety Analysis Set	
Table 14.3.2.5	Possibly Treatment-Related Treatment-emergent Adverse Events by System Organ Class and Preferred Term	Safety Analysis Set	
Table 14.3.2.6	Serious Possibly Treatment-Related Adverse Events by System Organ Class and Preferred Term	Safety Analysis Set	
Table 14.3.2.7	Possibly Treatment-Related Treatment-emergent Adverse Events by System Organ Class and Maximum Severity	Safety Analysis Set	
Table 14.3.2.8	Treatment-emergent Adverse Events leading to Discontinuation of Investigational Product by System Organ Class and Preferred Term	Safety Analysis Set	
Table 14.3.2.9	Adverse Events with Fatal Outcome by System Organ Class and Preferred Term	Safety Analysis Set	
Table 14.3.2.10	Adverse Events of Special Interest by System Organ Class and Preferred Term	Safety Analysis Set	
Table 14.3.3.1.1	Haematology Results by Time Point	Safety Analysis Set	
Table 14.3.3.1.2	Investigator Assessed Clinically Significant Postbaseline Haematology Results	Safety Analysis Set	
Table 14.3.3.1.3	Shift Summary of Haematology Results by Reference Range and Time Point	Safety Analysis Set	

Table 14.3.3.2.1	Biochemistry Results by Time Point	Safety Analysis Set	
Table 14.3.3.2.2	Investigator Assessed Clinically Significant Postbaseline Biochemistry Results	Safety Analysis Set	
Table 14.3.3.2.3	Shift Summary of Biochemistry Results by Reference Range and Time Point	Safety Analysis Set	X
Table 14.3.3.3.1	Quantitative Urinalysis Results by Time Point	Safety Analysis Set	

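### The tables of clinically significant laboratory results in SAP 12.6.3 do not separate abnormalities already present before dosing from new ones

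*SAP*

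**What the plan says.** SAP 12.6.3 makes the judgement the investigator's: "Clinical laboratory test values are assessed for clinical significance by the investigator". It then defines the count, "The number and percentage of subjects with post-baseline clinically significant values will be tabulated by treatment group", and the denominator: "The percentages will be calculated relative to the number of subjects with at least 1 post-baseline assessment". The outputs are Tables 14.3.3.1.2 (haematology), 14.3.3.2.2 (biochemistry) and 14.3.3.3.2 (urinalysis) in SAP Appendix 1. The biochemistry title reads "Investigator Assessed Clinically Significant Postbaseline Biochemistry Results". None of the three titles adds a condition on baseline.

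The same section uses the baseline in two other ways. One is numerical: "Descriptive statistics for clinical laboratory values (in SI units) and changes from baseline at each assessment time point will be presented by treatment group". The other is by reference range: "Laboratory results will be categorised as low, normal or high in relation to the local laboratory reference range, and shift tables from baseline".

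The general rule in Protocol 10.3 is: "If categorical variables are assessed both at and after baseline, then cross-tabulations will be presented by category at baseline". For the ECG, SAP 12.6.5 applies a rule of this kind to the reader's three-way judgement (normal, abnormal CS, abnormal not CS), shown as a shift from baseline. SAP 4.1 lists two changes from the protocol, and neither concerns the laboratory CS judgement.

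**The concern.** A subject whose result was CS before the first injection, and is judged CS again at a scheduled visit afterwards, enters the table exactly as a new case does. Some such subjects can pass eligibility. On liver disease, "a diagnosis of steatosis is permitted providing inclusion criterion 6 is met", and criterion 6 accepts ALT or AST up to 1.5 times the upper limit of normal. There is no numerical entry limit for GGT, glucose, creatinine, phosphate or platelets.

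Safety laboratory results are among the primary variables (Protocol 3.3.1, SAP 7.1). With about 10 subjects per arm, one or two persisting abnormalities that fall unevenly by chance can look like a difference between arms, and nothing in these tables would tell the reader otherwise.

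**Working it through.** The plan gives no figure on this point: no sample size calculation and no expected rate of CS results. The arm sizes are consistent: 5+10+5+5+10+10+5+10 = 60, which matches the planned total.

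**1. What is counted.** The numerator is subjects, each counted once. By SAP 8.3, unscheduled and repeat results stay out of summary tables, so only scheduled visits contribute. The flow chart has safety laboratory tests at screening and on Days 8, 29, 36, 57, 64, 85 and 225, with none on Day 1. The baseline result will therefore usually be the screening one. A persisting abnormality has six scheduled visits up to Day 85 at which it can be judged CS again.

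**2. Whether another laboratory table makes the separation.**
- Change from baseline is numerical and carries no CS judgement.
- The low/normal/high shift tables carry no CS judgement either. Take a result that is high but not CS at baseline, then high and CS later. The shift table shows high to high, and the CS table shows a case without saying that it is new.
- Listings allow reconstruction subject by subject, but give no tabulated count.

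No planned laboratory table separates new from pre-existing CS results.

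**3. Effect on the percentage.** Take an arm of 10, all with post-baseline data, with c subjects CS before and after dosing and e new cases. The SAP table shows (c+e)/10. A table restricted to subjects not CS at baseline shows e/(10−c).

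| c | e | SAP table | Not CS at baseline |
|---|---|---|---|
| 1 | 0 | 1/10 = 10.0% | 0/9 = 0% |
| 1 | 1 | 2/10 = 20.0% | 1/9 = 11.1% |
| 2 | 1 | 3/10 = 30.0% | 1/8 = 12.5% |

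**4. How often chance alone would show.** Let q be the share of subjects who are CS at baseline and again at a scheduled visit. The documents do not give q, so the values below are assumptions. With no new cases, the number in an arm is Binomial(10, q). Then P(at least one) = 1 − (1−q)^10. For two independent arms, P(difference ≥ k) is the sum of b(i)b(j) over |i−j| ≥ k, where b(x) = C(10,x) q^x (1−q)^(10−x).

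| Assumed q | At least one in a given arm | Two given arms differ by ≥ 1 | Two given arms differ by ≥ 2 |
|---|---|---|---|
| 2% | 18% | 30% | 3% |
| 5% | 40% | 54% | 11% |
| 10% | 65% | 69% | 24% |
| 20% | 89% | 78% | 39% |

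The higher values of q are more plausible for a whole panel than for one analyte. Per analyte, the lower rows are the more relevant ones.

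**The case against.** The case against is substantial, and it limits the size of the point.

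- **Adverse events.** Protocol 7.6.1.2 requires clinically relevant laboratory values or changes to be entered as adverse events. SAP 12.6.1 counts an event as treatment-emergent only if it is new or has worsened in severity or relatedness since the first dose. Medical judgement with a baseline condition therefore does reach the safety tables. This stands, with one limit: after Day 85 only serious events and events of special interest are collected (Protocol 9.2), so it covers the Day 225 laboratory results less well.
- **Protocol 10.9.6.** This laboratory-specific section asks for summary statistics, shift tables and a clinical-significance indicator in listings. The CS count can be read as an extra output. A reader might infer an undeclared breach of Protocol 10.3, but the documents do not settle that. What they do show is that the table sits badly with the general rule and with the SAP's own ECG table.
- **Decision role.** A reader might infer that these tables drive the choice of dose and formulation. Appendix 1 marks the treatment-emergent event table (14.3.2.2) and the biochemistry shift table (14.3.3.2.3) as top-line, and none of the three CS tables.
- **Eligibility.** Exclusions 5, 6 and 11 (relevant co-morbidity; relevant anaemia or leukopenia; any condition that might interfere with the study objectives) remove some baseline abnormalities. A raised ALT within the entry limit need not be CS.
- **Direction.** A reader might infer bias against the vaccine arms. The rule is identical in every arm, including placebo and IC31 alone, assessors are blinded, and nothing is tested.
- **Inclusiveness.** Counting all CS subjects cannot hide a signal, whereas a headline restricted to subjects not CS at baseline could drop someone who was CS and then worsened. This is a fair criticism of replacing the count. It does not apply if the total is kept and baseline-CS subjects have their own line.

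None of this supplies the missing split of the CS counts themselves.

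**Conclusion.** The point holds as a minor reporting gap. As written, the three CS tables mix persisting pre-dose abnormalities with new ones, and no other planned laboratory table separates them. The consequence is inflated counts and non-directional noise: 10 percentage points for each carried-over subject in an arm of 10.

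How often this happens cannot be known from the documents. The chance of a two-subject difference between two given arms runs from 3% to 39% as the assumed carry-over share goes from 2% to 20%. Those figures assume independent subjects, complete follow-up and no new cases.

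It would be too strong to say that every post-baseline CS value is counted: subjects are counted once, at scheduled visits, and only if the abnormality is again judged CS. It would also be too strong to say that these tables are the only laboratory information carrying medical judgement, because the adverse event tables carry it too.

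**What to change.** In SAP 12.6.3 and Tables 14.3.3.1.2, 14.3.3.2.2 and 14.3.3.3.2, for each analyte and treatment group:

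1. Cross-tabulate post-baseline CS (yes/no) by baseline CS (yes/no).
2. Keep the total count of subjects with a post-baseline CS result.
3. Add the number and percentage with a post-baseline CS result among subjects not CS at baseline.
4. Show subjects already CS at baseline on a separate line, so that any worsening among them stays visible.

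The cost is SAP wording, programming for three tables and slightly larger outputs. No new data are needed if the CS judgement was recorded for the baseline sample. The general wording of SAP 12.6.3 indicates that it was, but the eCRF should be checked, including the Cohort 1 data carried over from the earlier database (SAP 13.1).

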#### 12.6.4 Vital Signs

Descriptive statistics for vital signs (systolic and diastolic blood pressure, pulse rate and temperature) and their changes from baseline at each post-baseline visit and at the end of study will be presented by treatment group.

Individual vital signs results will be listed.

### 12.6.5 Electrocardiogram (ECG)

Shifts from baseline to follow-up in the reader's interpretation of each ECG result ('Normal', 'Abnormal Clinically Significant' or 'Abnormal not clinically significant') will be presented by treatment group. In addition, the reader's interpretation will be listed for each individual subject.

### 12.6.6 Physical Examination

A complete (or abbreviated) physical examination will be performed at the time points described in [Table 1](#). Abnormalities identified at the screening visit will be documented in the subject's source documents and on the medical history eCRF. Changes after the screening visit that are considered clinically significant by the investigator will be captured as AEs on the AE eCRF page. As such, any abnormalities will be included in the medical history or adverse events tables and listings. A listing indicating the date and time of physical examination will be produced.

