7.6.1.5 Physical examination

A physical examination will be performed by a physician at the times indicated in the flow chart (see **Error! Reference source not found.**). A full physical examination will be conducted at screening

including examination of weight and height, general appearance, eyes, ears, nose, throat, chest/respiratory system, heart/cardiovascular system, gastrointestinal system/liver, musculoskeletal system/extremities, dermatological system/skin, thyroid/neck, lymph nodes, and neurological system/psychiatric system.

A brief physical examination will be conducted at all other times including examination of general appearance, respiratory and cardiovascular systems and the abdomen, particularly the upper right quadrant. Any clinically relevant change in physical examination should be recorded as an AE.

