10.9.7 Other safety assessments

The Physical Examination will be summarised by treatment arm and time point.

Concomitant medications will be summarised by treatment arm, WHO drug class, generic name and indication.

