### 4.1 Changes from Protocol

Section 10.9.7 of the protocol calls for physical examination results to be summarised descriptively. As described later in the SAP, the completion of each physical exam will be listed only to avoid duplication of data.

The definition of the immunogenicity Analysis Set has been amended to include a criterion that subjects must have received all 3 planned doses of investigational product (IP) and with no important protocol deviations adjudicated as relevant by the medical team.

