 Prior to injection of IMP.

 Women of childbearing potential only. Serum pregnancy test will be performed at screening; a urine pregnancy test will be performed at other scheduled time points.

 A full physical examination will be conducted at screening and a brief physical examination will be performed at other time points indicated and will include examination of general appearance, injection site, respiratory and cardiovascular systems and the abdomen, particularly the upper right quadrant.

 Visit intervals are as follows:

- screening and randomisation: subjects must be screened -1 to 28 days ( $\pm 2$  days) and can be randomised to treatment up to 3 days prior to the first injection.
- first dose: Visits 1 and 2 must be done on Days 1 and 2, respectively; Visit 3 may be done within  $\pm 1$  day of Day 8.
- second dose: Visit 4 may be done 28 days ( $\pm 7$  days) after Visit 1; subjects must be contacted the day after Visit 4; Visits 5 should be done 7 ( $\pm 1$  day) days after Visit 4.
- third dose: Visit 6 may be done 28 days ( $\pm 7$  days) after Visit 4; subjects must be contacted the day after Visit 6; Visits 7 and 8 may be done 7 ( $\pm 1$  day) and 28 ( $\pm 1$  day) days after Visit 6.
- follow-up: Visit 9 must be done at 24 ( $\pm 28$  days) weeks after the last dose (Visit 6).

 PBMC samples for CMI; in consenting subjects HLA typing and other genomic analyses may also be performed.

 Only SAEs and AESIs need to be documented during Follow-up (Visit 9).

 Subjects will be contacted at approximately 4 week intervals during the follow-up phase.

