Listing 16.2.8.1	Laboratory Haematology Results and Change from Baseline	Safety Analysis Set
Listing 16.2.8.2	Laboratory Biochemistry Results and Change from Baseline	Safety Analysis Set
Listing 16.2.8.3	Laboratory Urinalysis Results and Change from Baseline	Safety Analysis Set
Listing 16.2.8.4	Pregnancy Test Results (Females of Childbearing Potential Only)	Safety Analysis Set
Listing 16.2.9	Vital Signs (Sitting)	Safety Analysis Set
Listing 16.2.10	Electrocardiogram Results	Safety Analysis Set
Listing 16.2.11.1	Injection Site Tolerability – Investigator Assessed	Safety Analysis Set
Listing 16.2.11.2	Injection Site Tolerability – Diary Card	Safety Analysis Set
Listing 16.2.12	Physical Examination Results	Safety Analysis Set
Listing 16.2.13	Telephone Calls	Safety Analysis Set
Listing	Legacy Data not Required by Protocol	Randomised Set

Sponsor: Altimune UK Ltd

Protocol no: FP02.2\_CS\_01

Statistical Analysis Plan

09-Mar-2018

16.2.14

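### SAP 4.1 and 12.6.6 drop the physical-examination summary because findings will appear as AEs, but this is not secured at Visit 9 (Day 225), where AE collection is limited to SAEs and AESIs

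*SAP*

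**What the plan says.** **Planned output.** Protocol section 10.9.7 states: "The Physical Examination will be summarised by treatment arm and time point".

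**Replacement.** SAP section 4.1 declares a change from this: "the completion of each physical exam will be listed only to avoid duplication of data". SAP section 12.6.6 gives the reasoning. Abnormalities at screening go to medical history. For later visits, "Changes after the screening visit that are considered clinically significant by the investigator will be captured as AEs on the AE eCRF page". It concludes: "As such, any abnormalities will be included in the medical history or adverse events tables and listings". What remains is described as follows: "A listing indicating the date and time of physical examination will be produced". Appendix 1 nevertheless titles that output (Listing 16.2.12) "Physical Examination Results".

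**Recording rule for examination changes.** Protocol section 7.6.1.5 states: "Any clinically relevant change in physical examination should be recorded as an AE". No visit is excepted.

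**Recording rule for Visit 9.** Note 8 to the flow chart, in both documents, reads "Only SAEs and AESIs need to be documented during Follow-up (Visit 9". Protocol section 9.2 likewise restricts collection after Day 85 to SAEs and AESIs, and the Visit 9 assessment list in protocol section 7.7 names only those two categories. AESIs are hepatic flares and autoimmune conditions (protocol section 9.1, Table 7). The same Visit 9 list includes a physical examination.

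**The concern.** A summary can be dropped as duplicate only if the same information appears somewhere else. Up to Day 85 that is plausible for clinically significant changes, because all AEs are collected. At Visit 9 the AE route is narrowed to SAEs and AESIs while the examination is still performed, so the SAP relies on a route that its own flow chart restricts.

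This is a first-in-man vaccine study, and Visit 9 holds the only scheduled examination after Day 85, covering the last 140 days (225 − 85). Flow-chart note 5 includes the injection site in the brief examination, and scheduled injection-site tolerability assessments end at Visit 7 (Day 64). A late local sign that is neither serious nor an AESI is the kind of finding that could be seen at that visit and not appear in the report.

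**Working it through.** No sample size, power or error-rate figure is involved. The check sets the rules side by side and adds some day arithmetic.

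**1. How many examinations are affected.** The flow chart and visit lists schedule examinations after the first dose on Days 2, 8, 29, 36, 57, 64, 85 and 225, which is 8. The Day 1 examination is pre-vaccination. One of the 8 (Day 225) falls after Day 85.

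**2. What happens to a Visit 9 finding that is clinically significant but neither serious nor an AESI.**

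- *If protocol sections 7.7 and 9.2 and note 8 govern:* no AE record is made. The medical history outputs do not help, because SAP 12.6.6 routes only screening abnormalities there. The examination listing, as described in SAP 12.6.6, shows date and time only.
- *If protocol section 7.6.1.5 and SAP 12.6.6 govern:* an AE is recorded. The next question is which outputs it reaches.

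**3. Which AE outputs a recorded finding reaches.** SAP 12.6.1 ends the treatment-emergent window 30 days after the last dose.

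- Nominal close of the window: Day 57 + 30 = Day 87.
- Visit 9, from protocol section 7.9: 24 ± 4 weeks after the last dose, so 20 × 7 = 140 to 28 × 7 = 196 days, nominally 24 × 7 = 168 days (Day 57 + 168 = Day 225).
- Smallest gap between close of the window and Visit 9: 140 − 30 = 110 days.

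The gap is measured from the last dose, so the ± 7-day dosing windows do not change it. An AE with onset at Visit 9 is never treatment-emergent. SAP 12.6.1 goes beyond the window only for SAEs and AESIs. The other AE tables in Appendix 1 cover treatment-emergent, serious, fatal or special-interest events, so this AE enters none of them. It does appear in the all-AE listing (16.2.7.1), and in the possibly-related listing (16.2.7.3) if so judged.

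**4. Comparison with the assurance.** SAP 12.6.6 promises the tables and listings. Under the first reading the finding reaches neither. Under the second it reaches listings but no table. The assurance fails at Day 225 under both.

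**The case against.** A reader might infer that every non-serious examination finding at Day 225 is reported nowhere. The documents do not support that, for three reasons.

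- Non-serious AESIs are recorded at Visit 9 and have their own table and listing, whatever their timing.
- Protocol section 7.6.1.5 and SAP 12.6.6 both send relevant changes to the AE page with no exception for Visit 9, and note 8 can be read as a minimum. Protocol section 9.2 is stricter. That is a conflict between rules, not proof that the finding is lost.
- The title of Listing 16.2.12 leaves open whether findings will be shown, although SAP 4.1 and 12.6.6 point to completion, date and time only. The eCRF is not available to settle it.

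The defence has further points. Protocol section 10.3 allows the SAP to change planned analyses if the change is described, and SAP 4.1 describes it. Limiting late AE collection is a design choice: the primary endpoints are unsolicited AEs through Day 85, and SAEs and AESIs through 6 months. The physical examination is not a listed endpoint, and the trial summary describes it as being for diagnoses only. Visit 9 laboratory tests, vital signs and ECG are reported separately, and liver signs are partly covered by the AESI definition and the liver tests. The injection site is named in flow-chart note 5 but not in the brief examination described in protocol section 7.6.1.5.

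All of this stands and keeps the point small. It does not restore the SAP's reason. A permitted change still needs a justification that holds at every visit it covers, and sites cannot follow both recording rules for the same finding.

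**Conclusion.** The point holds in a limited form. At Visit 9 the duplication argument in SAP 4.1 and 12.6.6 is not secured. A clinically significant finding that is neither serious nor an AESI may go unrecorded because the recording rules conflict. If it is recorded, it falls outside the treatment-emergent tables and appears in listings only.

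The size is minor: one of eight examinations after the first dose, in up to about 60 subjects, in the follow-up analysis only. The documents give no rate for such findings, so the number affected cannot be estimated. No hypothesis test depends on it.

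The conclusion assumes that the finding's onset is dated more than 30 days after the last dose, and that Listing 16.2.12 follows the SAP text rather than its title. If that listing does carry findings, reporting is largely secured, and what remains is the conflict between the recording rules and the absence from tables.

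**What to change.** 1. Reconcile the two recording rules for Visit 9: protocol section 7.6.1.5 and SAP 12.6.6 on one side, protocol sections 7.7 and 9.2 and flow-chart note 8 on the other.
2. In SAP 4.1, limit the duplication reason to visits up to Day 85, and qualify the sentence in 12.6.6 in the same way.
3. For Visit 9, show clinically significant examination findings in Listing 16.2.12 as well as date and time, and make the SAP text agree with the listing's title. Alternatively, keep the protocol 10.9.7 summary for that visit.

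Recording the finding as an AE would not by itself put it in a table, because of the 30-day window, so step 3 is needed whichever way step 1 is settled.

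The cost is small. The examination is already performed, so the work is a listing change and, if the eCRF holds only completion and date, a field for the finding. Amending note 8 and section 9.2 would also need a protocol clarification. Keeping the narrow AE rule and reporting the findings through Listing 16.2.12 avoids widening AE collection, but section 7.6.1.5 would then need its own clarification for Visit 9.
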